1.7.1 Clinical Efficacy of Atezolizumab in SCCHN

In the Phase I PCD4989g study, 10 patients with metastatic SCCHN regardless of PD-L1 status were initially enrolled (Bahleda et al. 2017). Once PD-L1 was identified as a potential biomarker, 22 additional patients were enrolled and received atezolizumab IV Q3W (15 mg/kg or 20 mg/kg, or 1200 mg). Objective response and disease progression were determined using investigator-assessed RECIST v1.1.

With a minimum 14-month follow-up period, there were 32 efficacy-evaluable patients with SCCHN (n=7 [IC0/1: <5% PD-L1 expression on IC], n=25 [IC2/3: ≥5% PD-L1 expression on IC]) as of 31 December 2016. Of these 32 patients, 84% were male, 66% had an Eastern Cooperative Oncology Group (ECOG) Performance Status of 1, and 34% had an ECOG Performance Status of 0. The median age was 62 years (range: 32–78 years), patients were heavily pre-treated (53% had ≥ 2 prior lines of therapy), and 66% were current or former tobacco users. Primary tumor sites included the oropharynx (56%), oral cavity (22%), nasopharynx (13%), larynx (6%), and hypopharynx (3%). Of the 28 non-nasopharyngeal patients, 46% tested positive for HPV, 43% tested negative for HPV, and 11% had unknown HPV status (Colevas et al. 2018).

The confirmed ORR of the 32 enrolled patients was 22% (95% CI: 9.3% to 40.0%), and the median DOR was 7.4 months (95% CI: 2.8 to 45.8 months). The median PFS was 2.6 months (range: 0.5–48.4 months), and the median OS was 6.0 months (range: 0.5–51.6 months, censored value) (Colevas et al. 2018).

The encouraging response and long-term survival shown in this heavily pre-treated advanced recurrent/metastatic SCCHN cohort suggests that patients may derive clinical benefit from atezolizumab treatment.

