Patients who discontinue study treatment (for any reason, including, but not limited to, clinical decline or toxicity) in the absence of radiographic disease progression per RECIST v1.1 will continue scheduled tumor assessments at the frequency described above until radiographic disease progression per RECIST v1.1, withdrawal of consent, death, or study termination by the Sponsor, whichever occurs first, regardless of whether a patient starts a new anti-cancer therapy.

Objective response at a single timepoint will be determined by the investigator according to RECIST v1.1 ([Appendix 4](#)).

In order not to confound the OS endpoint, crossover will not be allowed from Arm B (atezolizumab plus placebo) to Arm A (atezolizumab plus tiragolumab).

Patients will be asked to complete PRO questionnaires during the study treatment and at the study treatment discontinuation visit (see [Appendix 2](#) for PRO schedule).

Serum samples will be collected to monitor atezolizumab and tiragolumab PK and to detect the presence of antibodies to atezolizumab and tiragolumab. [REDACTED]

Safety assessments will include the incidence, nature, and severity of adverse events, and other protocol-specified tests, such as laboratory abnormalities, that are deemed critical to the safety evaluation of the study.

After study treatment discontinuation, survival follow-up information will be collected by means of telephone calls, patient medical records, and/or clinic visits approximately every 3 months until death, loss to follow-up, or study termination by the Sponsor, whichever occurs first (see Section [4.6.1](#)). All patients will be periodically contacted for survival and new anti-cancer therapy information unless the patient requests to be withdrawn from survival follow-up (this request must be documented in the source documents and signed by the investigator). If the patient withdraws from survival follow-up, study staff may use a public information source (e.g., county records) to obtain information about survival status.

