4.5.9 Clinical Outcome Assessments

PRO instruments will be completed to more fully characterize the clinical profile of atezolizumab plus tiragolumab and atezolizumab plus placebo. In addition, PRO instruments will enable the capture of each patient's direct experience with atezolizumab plus tiragolumab and atezolizumab plus placebo.

PRO data will be collected through use of the following instruments:

- PROMIS® Item Bank v2.0–Physical Functioning–Short Form 10b
- [REDACTED]
- [REDACTED]
- [REDACTED]
- Patient Global Impression of Severity (PGI-S)
- Patient Global Impression of Change and its Importance (PGI-CI)
- Most Important Symptoms (MIS)
- [REDACTED]

PRO questionnaires (i.e., PROMIS®, PGI-S/PGI-CI, MIS, and [REDACTED]) will be completed during treatment and at the treatment discontinuation visit, refer to [Appendix 2](#) for schedule of PRO assessments.

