6.4.2.4 Patient-Reported Outcomes

TTCD for physical functioning using the PROMIS® Item Bank v2.0–Physical Functioning–Short Form 10b is defined as the time from the date of randomization until the first confirmed clinically meaningful deterioration. Confirmed clinically meaningful deterioration in physical function is defined as a clinically meaningful decrease from baseline that must be held for at least two consecutive assessments, or an initial clinically meaningful decrease from baseline followed by death. A T-score change >4 points is considered to be clinically meaningful for the physical functioning subscale score (Yost et al. 2011).

TTCD will be assessed in all randomized patients who received at least one dose of study treatment. Patients will be grouped based on actual treatment received. Patients who have not experienced a confirmed clinically meaningful deterioration at the clinical cutoff date will be censored at the last time when they completed an assessment. If no baseline or post-baseline assessment is performed, patients will be censored at the randomization date. TTCD [REDACTED] will be analyzed using the same methods as for PFS.

[REDACTED]

[REDACTED]

[REDACTED]

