Appendix 2 Schedule of Patient-Reported Outcome Assessments

Visit	Timepoint	Sample Type(s)
Cycles 1 and 2, Day 1	Predose and prior to disease status assessments ^a	
 PROMIS® Item Bank v2.0–Physical Functioning–Short Form 10b [REDACTED] [REDACTED] [REDACTED] [REDACTED] [REDACTED] MIS PGI-S
Cycle 3, Day 1 and every other cycle until treatment discontinuation (i.e., Cycles 5, 7, 9, etc.)	Predose and prior to disease status assessments ^a	
 [REDACTED] MIS PGI-S PGI-CI
Cycle 4, Day 1 and every other cycle until treatment discontinuation (i.e., Cycles 6, 8, 10, etc.)	Predose and prior to disease status assessments ^a	
 PROMIS® Item Bank v2.0–Physical Functioning–Short Form 10b [REDACTED] [REDACTED] [REDACTED] [REDACTED] PGI-S PGI-CI
Treatment discontinuation visit	At visit	
 As indicated based on alternating schedule of assessment per cycle.

MIS=Most Important Symptoms; PGI-CI=Patient Global Impression of Change and its Importance; PGI-S=Patient Global Impression of Severity; PK=pharmacokinetic; PRO=patient-reported outcome; [REDACTED]

PROMIS =Patient-Reported Outcomes Measurement Information System

^a To be completed before the patient receives any information on disease status and prior to the performance of non-PRO assessments and the administration of study treatment. Study personnel should review all questionnaires for completeness before the patient leaves the investigational site. In scenarios where other clinical activities performed ≤ 96 hours before the visit dates (e.g., those specified in [Appendix 1](#) footnote h) are intended for treatment determination, PROs can be completed ≤ 96 hours before the scheduled visit, prior to those clinical activities.

Appendix 4

Response Evaluation Criteria in Solid Tumors, Version 1.1 (RECIST v1.1)

Selected sections from the Response Evaluation Criteria in Solid Tumors, Version 1.1 (RECIST v1.1), (Eisenhauer et al. 2009) are presented below, with slight modifications from the original publication and the addition of explanatory text as needed for clarity.¹

TUMOR MEASURABILITY

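### PROMIS Physical Functioning is collected at the treatment discontinuation visit only when the alternating cycle schedule points to it, so some late decreases cannot be confirmed for TTCD

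*Combined protocol and SAP*

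**What the plan says.** **Schedule.** Appendix 2 lists PROMIS Physical Functioning 10b in the row "Cycles 1 and 2, Day 1" and again from Cycle 4 at every even cycle. The row for Cycles 3, 5, 7 and so on does not show it. That row has one redacted item, but the form is printed openly in the other two rows, so the redaction is unlikely to hide it. For the treatment discontinuation visit the entry is "As indicated based on alternating schedule of assessment per cycle". No PRO is scheduled after that visit.

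**General text.** Section 4.5.9 names PROMIS among the questionnaires that "will be completed during treatment and at the treatment discontinuation visit, refer to" Appendix 2 for the schedule. Section 3.1 says "Patients will be asked to complete PRO questionnaires during the study treatment and at the study treatment discontinuation visit" and also points to Appendix 2.

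**Endpoint.** Section 2.1.2 lists TTCD as a secondary endpoint. Under Section 6.4.2.4 a clinically meaningful decrease "must be held for at least two consecutive assessments, or an initial clinically meaningful decrease from baseline followed by death". No time limit is given for the death. Patients without a confirmed event at the cutoff "will be censored at the last time when they completed an assessment".

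**Scans.** Section 4.5.6 sets tumor assessments every 6 weeks to Week 30, then every 9 weeks. Section 4.6.1 allows the visit that shows progression to serve as the discontinuation visit.

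**The concern.** A decrease first recorded on the last on-treatment form needs one more form to count. The discontinuation visit is the last chance to collect it, and under Appendix 2 the form may not be due there. Patients stop largely because they progress or decline, so censoring them at the last completed form is unlikely to be independent of their physical function. TTCD would then tend to look longer than it is. The endpoint also comes to depend on how long patients are followed for death, because death is the only other route to an event. Finally, a site that reads Section 4.5.9 may give PROMIS to every patient at discontinuation while a site that reads Appendix 2 does not.

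**Working it through.** The documents state no power, event count or expected censoring for TTCD in the visible text, so there is no figure to reproduce. All rates below are assumptions.

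**Inputs.** Section 1.7.1 reports for atezolizumab in previously treated SCCHN: "The median PFS was 2.6 months". Section 1.6.2.3 gives 5.5 months as the longer median in the NSCLC study. Both are used as medians *m* for time on treatment. Section 1.1 gives a median survival of 6–15 months. One cycle is 21/30.4375 = 0.690 months.

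**Step 1: calendar.** Cycle = week/3 + 1. Weeks 6, 12, 18, 24 and 30 give Cycles 3, 5, 7, 9 and 11, none with PROMIS. After that, Week 39 is Cycle 14 and Week 48 is Cycle 17, so scans alternate between cycles with and without the form.

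**Step 2: stopping unrelated to scans.** Let q = 2^(−0.690/m). The probability that the visit falls on cycle n ≥ 2 is (1−q)q^(n−2). Summed over odd n, this is q/(1+q).
- m = 2.6: q = 0.832, giving 0.832/1.832 = 45%.
- m = 5.5: q = 0.917, giving 0.917/1.917 = 48%.

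**Step 3: stopping on nominal scan days.** Let S(w) = 2^(−(7w/30.4375)/m), and sum the probability over scan weeks that land on odd cycles.
- m = 2.6: 1 − S(30) = 0.841, plus later odd-cycle scans of 0.058, gives 90%.
- m = 5.5: 0.581 + 0.181 gives 76%.

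**Step 4: death rule.** With median survival after stopping of 6 to 15 months, 1 − 2^(−6/15) = 24% to 1 − 2^(−6/6) = 50% die within 6 months. Within 24 months it is 67–94%. Unconfirmed decreases in these patients become events.

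**Step 5: simulation.** Eight combinations were run with one million patients each: median time on treatment 2.6 or 5.5 months, median survival after stopping 6 or 10 months, and median time to a lasting decrease 4 or 8 months, all exponential and independent. Cutoffs were 9 and 24 months from randomization. Figures are percentages of all patients, as ranges over the eight combinations.

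| | Appendix 2 as written | Form at every discontinuation visit |
|---|---|---|
| *Stopping on scan days* | | |
| Observed, unconfirmed by 9 months | 5.3–11.9 | 3.2–6.8 |
| Observed, unconfirmed by 24 months | 6.4–12.2 | 3.8–7.0 |
| Of these, censored at 9 months | 3.3–8.1 | 2.0–4.5 |
| Of these, censored at 24 months | 0.8–3.0 | 0.5–1.7 |
| *Stopping unrelated to scans* | | |
| Observed, unconfirmed by 9 months | 5.4–12.0 | 4.3–9.6 |
| Observed, unconfirmed by 24 months | 6.4–12.3 | 4.9–9.8 |
| Of these, censored at 9 months | 3.1–8.0 | 2.4–6.3 |
| Of these, censored at 24 months | 0.8–3.0 | 0.6–2.3 |

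**The case against.** **Section 4.5.9.** A reader might infer that it says the opposite of Appendix 2. It does not: the same sentence sends the reader to Appendix 2, as does Section 3.1. Read literally for every instrument, it would also clash with Appendix 2 over the Most Important Symptoms questionnaire, which is absent from the even-cycle row. This is general text to be reconciled with a schedule, not a direct contradiction.

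**Death rule.** A reader might infer that every unconfirmed decrease is censored. Section 6.4.2.4 counts a decrease followed by death as an event, and in a disease with this survival that recovers most of them by 24 months.

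**Early stopping.** It is tempting to take the share who stop before Cycle 4 as the loss: with a 2.6-month median, 1 − 2^(−2.07/2.6) = 42%. That counts patients who stop, not deteriorations that are lost. Of the 42%, about 17% stop before Cycle 2 and have no post-baseline form, so one form at discontinuation cannot confirm anything for them; about 26% have exactly one. Patients who stop between Cycles 4 and 6 already have two post-baseline forms.

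**Inputs.** The medians come from previously treated SCCHN and from NSCLC, whereas this trial is first-line SCCHN. The ±7-day scan window, late scan reads and treatment beyond progression (Section 3.1.1) all lower the 76–90% figure.

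**Reading of Appendix 2.** The entry could mean the set for the cycle in which the visit falls, as assumed here, or the set for the last cycle started. On the second reading, a patient stopped at a Week 6 scan, before Cycle 3 dosing, would get PROMIS, and the scan-day figures reverse to 100 − 90 = 10% and 100 − 76 = 24%. That objection stands as a limit on the size. It also shows that the entry is unclear.

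**Between-arm bias.** A reader might infer that the arm comparison is biased. Both arms share one blinded schedule, TTCD is summarized by arm with Kaplan–Meier methods, and the visible text describes no between-arm test for it. A difference would need unequal time on treatment and is not quantified here.

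**Conclusion.** The point holds in a limited form. Appendix 2 makes the last PROMIS assessment depend on the cycle, and on the natural reading the scan calendar pushes progression visits onto cycles without it. About 6–12% of patients would have a decrease that is seen but not confirmed on a second form. About 3–8% of all patients would be censored for this reason at a 9-month cutoff, and about 1–3% at 24 months.

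These figures rest on exponential times, on medians borrowed from other populations, and on deterioration independent of progression; the documents give no deterioration rate. The size also depends on the TTCD cutoff, because a longer follow-up lets the death rule absorb most of the loss. TTCD is one of several secondary endpoints, and the primary ORR analysis is untouched. The case for acting is that the correction is cheap and removes an ambiguity for sites.

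**What to change.** - Amend the last row of Appendix 2 so that every patient completes PROMIS Physical Functioning 10b at the treatment discontinuation visit, whatever the cycle number, and align Sections 3.1 and 4.5.9 with it.
- State in Section 6.4.2.4 that this form can serve as the second consecutive assessment confirming an earlier decrease. State there also how an unconfirmed decrease on the final form is handled, and whether a time window applies to a later death.

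Unconfirmed decreases fall to about 3–7% of patients when stopping follows the scan calendar, and to about 4–10% when it does not. The remedy is partial: a decrease first seen at the discontinuation visit still has no later form to confirm it. The cost is ten paper items, a few minutes of patient time at a visit that already takes place, and short text changes.

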Appendix 4: Response Evaluation Criteria in Solid Tumors, Version 1.1 (RECIST v1.1)

there is definitely a new lesion, progression should be declared using the date of the initial scan.

CRITERIA FOR OVERALL RESPONSE AT A SINGLE TIMEPOINT

Table 1 provides a summary of the overall response status calculation at each response assessment timepoint for patients who have measurable disease at baseline.

Table 1 Criteria for Overall Response at a Single Timepoint: Patients with Target Lesions (with or without Non-Target Lesions)

Target Lesions	Non-Target Lesions	New Lesions	Overall Response
CR	CR	No	CR
CR	Non-CR/non-PD	No	PR
CR	Not all evaluated	No	PR
PR	Non-PD or not all evaluated	No	PR
SD	Non-PD or not all evaluated	No	SD
Not all evaluated	Non-PD	No	NE
PD	Any	Yes or no	PD
Any	PD	Yes or no	PD
Any	Any	Yes	PD

CR=complete response; NE=not evaluable; PD=progressive disease; PR=partial response; SD=stable disease.

MISSING ASSESSMENTS AND NOT-EVALUABLE DESIGNATION

When no imaging/measurement is done at all at a particular timepoint, the patient is not evaluable at that timepoint. If measurements are made on only a subset of target lesions at a timepoint, usually the case is also considered not evaluable at that timepoint, unless a convincing argument can be made that the contribution of the individual missing lesions would not change the assigned timepoint response. This would be most likely to happen in the case of PD. For example, if a patient had a baseline sum of 50 mm with three measured lesions and during the study only two lesions were assessed, but those gave a sum of 80 mm, the patient will have achieved PD status, regardless of the contribution of the missing lesion.

SPECIAL NOTES ON RESPONSE ASSESSMENT

Patients with a global deterioration in health status requiring discontinuation of treatment without objective evidence of disease progression at that time should be reported as "symptomatic deterioration." Every effort should be made to document objective

Appendix 4: Response Evaluation Criteria in Solid Tumors, Version 1.1 (RECIST v1.1)

progression even after discontinuation of treatment. Symptomatic deterioration is not a descriptor of an objective response; it is a reason for stopping study therapy. The objective response status of such patients is to be determined by evaluation of target and non-target lesions as shown in [Table 1](#).

For equivocal findings of progression (e.g., very small and uncertain new lesions; cystic changes or necrosis in existing lesions), treatment may continue until the next scheduled assessment. If at the next scheduled assessment, progression is confirmed, the date of progression should be the earlier date when progression was suspected.

REFERENCES

Appendix 5

Eastern Cooperative Oncology Group Performance Status Scale

Grade	Description
0	Fully active, able to carry on all predisease performance without restriction
1	Restricted in physically strenuous activity but ambulatory and able to carry out work of a light or sedentary nature; e.g., light housework or office work
2	Ambulatory and capable of all self-care but unable to carry out any work activities; up and about > 50% of waking hours
3	Capable of only limited self-care, confined to a bed or chair > 50% of waking hours
4	Completely disabled; cannot carry on any self-care; totally confined to bed or chair
5	Dead

Appendix 6

[figure not shown]
Patient-Reported Outcomes Measurement Information System®: PROMIS® Item Bank v2.0–Physical Function–Short Form 10b

[figure not shown]
PROMIS® Item Bank v2.0 – Physical Function – Short Form 10b

[figure not shown]
Physical Function – Short Form 10b

Please respond to each question or statement by marking one box per row.

		Without any difficulty	With a little difficulty	With some difficulty	With much difficulty	Unable to do
PFA11	Are you able to do chores such as vacuuming or yard work?.....	 5	 4	 3	 2	 1
PFA58	Are you able to get in and out of a car?	 5	 4	 3	 2	 1
PFA21	Are you able to go up and down stairs at a normal pace?	 5	 4	 3	 2	 1
PFA53	Are you able to run errands and shop?	 5	 4	 3	 2	 1
PFA8	Are you able to bend down and pick up clothing from the floor?.....	 5	 4	 3	 2	 1
PFR2b1	Are you able to lift 10 pounds (5 kg) above your shoulder?	 5	 4	 3	 2	 1
		Not at all	Very little	Somewhat	Quite a lot	Cannot do
PFA1	Does your health now limit you in doing vigorous activities, such as running, lifting heavy objects, participating in strenuous sports?.....	 5	 4	 3	 2	 1
PFA8	Does your health now limit you in bathing or dressing yourself?	 5	 4	 3	 2	 1
PFR3	Does your health now limit you in putting a trash bag outside?	 5	 4	 3	 2	 1
PFR44	Does your health now limit you in doing moderate activities, such as moving a table, pushing a vacuum cleaner, bowling, or playing golf?	 5	 4	 3	 2	 1

Appendix 10

Patient Global Impression of Severity (PGI-S)

Patient Global Impression of Severity (PGI-S)

Please choose the response below that best describes the severity of your overall status over the past week.

- | | |
|-------------|--------------------------|
| None |  |
| Mild |  |
| Moderate |  |
| Severe |  |
| Very severe |  |

Appendix 11

Patient Global Impression of Change and its Importance (PGI-CI)

Patient Global Impression of Change (PGI-C)

Since the start of the study, my overall status is:

- | | |
|--------------------|--------------------------|
| Very much improved |  |
| Much improved |  |
| Minimally improved |  |
| No change |  |
| Minimally worse |  |
| Much worse |  |
| Very much worse |  |

Patient-reported Importance of Change

In the previous question, you reported the change you have experienced since starting this trial.
Was this change important to you?

- | | |
|----------------|--------------------------|
| Yes |  |
| No |  |
| Not applicable |  |
- (selected *No change* in PGI-C)

[figure not shown]
Appendix 12

[figure not shown]
Most Important Symptoms

Which issues have been the most important to you during the past 7 days?

Check ☒ up to 4 boxes.

- | | | |
|--|---|--|
|  Chewing or swallowing |  Constipation |  Coughing |
|  Diarrhoea |  Dry mouth or sticky saliva |  Dry or itchy skin |
|  Loss of appetite |  Nausea or vomiting |  Pain |
|  Skin rash |  Disturbed sleep |  Speech |
|  Swelling |  Taste or smell |  Tired / fatigue |

[figure not shown]

Appendix 14

Preexisting Autoimmune Diseases and Immune Deficiencies

Patients should be carefully questioned regarding their history of acquired or congenital immune deficiencies or autoimmune disease. Patients with any history of immune deficiencies or autoimmune disease listed in the table below are excluded from participating in the study. Possible exceptions to this exclusion could be patients with a medical history of such entities as atopic disease or childhood arthralgias where the clinical suspicion of autoimmune disease is low. Patients with a history of autoimmune-related hypothyroidism on a stable dose of thyroid replacement hormone may be eligible for this study. In addition, transient autoimmune manifestations of an acute infectious disease that resolved upon treatment of the infectious agent are not excluded (e.g., acute Lyme arthritis). Caution should be used when considering atezolizumab for patients who have previously experienced a severe or life-threatening skin adverse reaction or pericardial disorder while receiving another immunostimulatory anti-cancer agent. The Medical Monitor is available to advise on any uncertainty over autoimmune exclusions.

Autoimmune Diseases and Immune Deficiencies

Appendix 15

Anaphylaxis Precautions

These guidelines are intended as a reference and should not supersede pertinent local or institutional standard operating procedures.

REQUIRED EQUIPMENT AND MEDICATION

The following equipment and medication are needed in the event of a suspected anaphylactic reaction during study treatment infusion:

- Monitoring devices: ECG monitor, blood pressure monitor, oxygen saturation monitor, and thermometer
- Oxygen
- Epinephrine for subcutaneous, intramuscular, intravenous, and/or endotracheal administration in accordance with institutional guidelines
- Antihistamines
- Corticosteroids
- Intravenous infusion solutions, tubing, catheters, and tape

PROCEDURES

In the event of a suspected anaphylactic reaction during study treatment infusion, the following procedures should be performed:

1. Stop the study treatment infusion.
2. Call for additional medical assistance.
3. Maintain an adequate airway.
4. Ensure that appropriate monitoring is in place, with continuous ECG and pulse oximetry monitoring if possible.
5. Administer antihistamines, epinephrine, or other medications and IV fluids as required by patient status and as directed by the physician in charge.
6. Continue to observe the patient and document observations.

Appendix 16

Risks Associated with Atezolizumab and/or Tiragolumab and Guidelines for Management of Adverse Events Associated with Atezolizumab and/or Tiragolumab

Toxicities associated or possibly associated with atezolizumab and/or tiragolumab treatment should be managed according to standard medical practice. Additional tests, such as autoimmune serology or biopsies, should be used to evaluate for a possible immunogenic etiology.

[figure not shown]
Although most immune-mediated adverse events observed with immunomodulatory agents have been mild and self-limiting, such events should be recognized early and treated promptly to avoid potential major complications. Discontinuation of atezolizumab and/or tiragolumab may not have an immediate therapeutic effect, and in severe cases, immune-mediated toxicities may require acute management with topical corticosteroids, systemic corticosteroids, or other immunosuppressive agents.

Patients and family caregivers should receive timely and up-to-date information about immunotherapies, their mechanism of action, and the clinical profile of possible immune-related adverse events prior to initiating therapy and throughout treatment and survival follow-up. There should be a high level of suspicion that new symptoms are treatment related.

The following are general recommendations for management of any other adverse events that may occur and are not specifically listed in the following subsections.

- [REDACTED]
- [REDACTED]
- [REDACTED]
- [REDACTED]
- [REDACTED]
- [REDACTED]
- The investigator should consider the benefit–risk balance for a given patient prior to further administration of atezolizumab and tiragolumab. [REDACTED]

Appendix 16: Risks Associated with Atezolizumab and/or Tiragolumab and Guidelines for Management of Adverse Events Associated with Atezolizumab and/or Tiragolumab

[figure not shown]

DOSE MODIFICATIONS

There will be no dose modifications for atezolizumab and tiragolumab in this study.

TREATMENT INTERRUPTION

Atezolizumab and tiragolumab treatment may be temporarily suspended in patients experiencing toxicity considered to be related to study treatment. 

 The decision to re-challenge patients with atezolizumab and tiragolumab should be based on the investigator's benefit-risk assessment and documented by the investigator. The Medical Monitor is available to advise as needed. Atezolizumab and tiragolumab treatment may be suspended for reasons other than toxicity (e.g., surgical procedures). The acceptable length of treatment interruption must be based on the investigator's benefit-risk assessment and in alignment with the protocol requirements for the duration of treatment and documented by the investigator. The Medical Monitor is available to advise as needed.

MANAGEMENT GUIDELINES

PULMONARY EVENTS

Pulmonary events may present as new or worsening cough, chest pain, fever, dyspnea, fatigue, hypoxia, pneumonitis, and pulmonary infiltrates. Patients will be assessed for pulmonary signs and symptoms throughout the study.

All pulmonary events should be thoroughly evaluated for other commonly reported etiologies such as pneumonia or other infection, lymphangitic carcinomatosis, pulmonary embolism, heart failure, chronic obstructive pulmonary disease, or pulmonary hypertension. Coronavirus disease 2019 (COVID-19) evaluation should be performed

Appendix 16: Risks Associated with Atezolizumab and/or Tiragolumab and Guidelines for Management of Adverse Events Associated with Atezolizumab and/or Tiragolumab

[figure not shown]
[figure not shown]
[figure not shown]
[figure not shown]
[figure not shown]
[figure not shown]
[figure not shown]
[figure not shown]
[figure not shown]
[figure not shown]
[figure not shown]
[figure not shown]
[figure not shown]

per institutional guidelines where relevant. Management guidelines for pulmonary events are provided in [Table 1](#).

Table 1 Management Guidelines for Pulmonary Events, Including Pneumonitis

Event	Management

	

	

a	
b	
c	
d	

Appendix 16: Risks Associated with Atezolizumab and/or Tiragolumab and Guidelines for Management of Adverse Events Associated with Atezolizumab and/or Tiragolumab

Table 1 Management Guidelines for Pulmonary Events, Including Pneumonitis (cont.)

Event	Management
	
• • • • • • 
 a	
 b	
 c	
 d	

Appendix 16: Risks Associated with Atezolizumab and/or Tiragolumab and Guidelines for Management of Adverse Events Associated with Atezolizumab and/or Tiragolumab

HEPATIC EVENTS

Patients eligible for study treatment must have adequate liver function, as manifested by measurements of total bilirubin and hepatic transaminases; liver function will be monitored throughout study treatment. Management guidelines for hepatic events are provided in [Table 2](#).

Patients with right upper-quadrant abdominal pain and/or unexplained nausea or vomiting should have liver function tests (LFTs) performed immediately and reviewed before administration of the next dose of study drug.

For patients with elevated LFTs, concurrent medication, viral hepatitis, and toxic or neoplastic etiologies should be considered and addressed, as appropriate.

Appendix 16: Risks Associated with Atezolizumab and/or Tiragolumab and Guidelines for Management of Adverse Events Associated with Atezolizumab and/or Tiragolumab

Table 2 Management Guidelines for Hepatic Events

Event	Management
[REDACTED]	
 • [REDACTED] • [REDACTED]
[REDACTED]	
All events:
 
 • [REDACTED] • [REDACTED] • [REDACTED] • [REDACTED] • [REDACTED] • [REDACTED]
[REDACTED]	
 • [REDACTED] • [REDACTED] • [REDACTED] • [REDACTED] • [REDACTED]

a [REDACTED]

b [REDACTED]

c [REDACTED]

Appendix 16: Risks Associated with Atezolizumab and/or Tiragolumab and Guidelines for Management of Adverse Events Associated with Atezolizumab and/or Tiragolumab

[figure not shown]
[figure not shown]
[figure not shown]
[figure not shown]

[figure not shown]
[figure not shown]
[figure not shown]
[figure not shown]
[figure not shown]
[figure not shown]
[figure not shown]
GASTROINTESTINAL EVENTS

Management guidelines for diarrhea or colitis are provided in [Table 3](#).

[figure not shown]
[figure not shown]
[figure not shown]
All events of diarrhea or colitis should be thoroughly evaluated for other more common etiologies. For events of significant duration or magnitude or associated with signs of systemic inflammation or acute-phase reactants (e.g., increased C-reactive protein, platelet count, or bandemia): Perform sigmoidoscopy (or colonoscopy, if appropriate) with colonic biopsy, with three to five specimens for standard paraffin block to check for inflammation and lymphocytic infiltrates to confirm colitis diagnosis.

Appendix 16: Risks Associated with Atezolizumab and/or Tiragolumab and Guidelines for Management of Adverse Events Associated with Atezolizumab and/or Tiragolumab

Table 3 Management Guidelines for Gastrointestinal Events (Diarrhea or Colitis)

Event	Management
	
• • • • 
	
• • • • • • • 

GI= gastrointestinal.

a	
b	
c	

Appendix 16: Risks Associated with Atezolizumab and/or Tiragolumab and Guidelines for Management of Adverse Events Associated with Atezolizumab and/or Tiragolumab

Table 3 Management Guidelines for Gastrointestinal Events (Diarrhea or Colitis) (cont.)

Event	Management

 

 

 
	

 

 

 
	

GI=gastrointestinal.

3

b

C

Appendix 16: Risks Associated with Atezolizumab and/or Tiragolumab and Guidelines for Management of Adverse Events Associated with Atezolizumab and/or Tiragolumab

ENDOCRINE EVENTS

Management guidelines for endocrine events are provided in [Table 4](#).

Patients with unexplained symptoms such as headache, fatigue, myalgias, impotence, constipation, or mental status changes should be investigated for the presence of thyroid, pituitary, or adrenal endocrinopathies. Patients should be referred to an endocrinologist if an endocrinopathy is suspected. Thyroid-stimulating hormone (TSH) and free triiodothyronine and thyroxine levels should be measured to determine whether thyroid abnormalities are present. Pituitary hormone levels and function tests (e.g., TSH, growth hormone, luteinizing hormone, follicle-stimulating hormone, testosterone, prolactin, adrenocorticotrophic hormone [ACTH] levels, and ACTH stimulation test) and magnetic resonance imaging (MRI) of the brain (with detailed pituitary sections) may help to differentiate primary pituitary insufficiency from primary adrenal insufficiency.

Appendix 16: Risks Associated with Atezolizumab and/or Tiragolumab and Guidelines for Management of Adverse Events Associated with Atezolizumab and/or Tiragolumab

Table 4 Management Guidelines for Endocrine Events

Event	Management
[REDACTED]	
• [REDACTED]• [REDACTED]• [REDACTED]
[REDACTED]	
[REDACTED]	
[REDACTED]	
[REDACTED]	
[REDACTED]	
[REDACTED]	
[REDACTED]	
[REDACTED]	
[REDACTED]	
[REDACTED]	

a

b

c

Appendix 16: Risks Associated with Atezolizumab and/or Tiragolumab and Guidelines for Management of Adverse Events Associated with Atezolizumab and/or Tiragolumab

Table 4 Management Guidelines for Endocrine Events (cont.)

Event	Management
[REDACTED]	[REDACTED] 
[REDACTED][REDACTED][REDACTED] [REDACTED] 
[REDACTED][REDACTED]
[REDACTED]	
[REDACTED][REDACTED][REDACTED][REDACTED]
[REDACTED]	
[REDACTED][REDACTED][REDACTED][REDACTED][REDACTED]

a

b

c

Table 4 Management Guidelines for Endocrine Events (cont.)

Event	Management
	
 • • • •
	
 • •

a

b

C

Appendix 16: Risks Associated with Atezolizumab and/or Tiragolumab and Guidelines for Management of Adverse Events Associated with Atezolizumab and/or Tiragolumab

Table 4 Management Guidelines for Endocrine Events (cont.)

Event	Management
[REDACTED]	
• [REDACTED]• [REDACTED]• [REDACTED]• [REDACTED]• [REDACTED]
[REDACTED]	
• [REDACTED]• [REDACTED]• [REDACTED]• [REDACTED]• [REDACTED]• [REDACTED]• [REDACTED]• [REDACTED]• [REDACTED]

a

b

c

Appendix 16: Risks Associated with Atezolizumab and/or Tiragolumab and Guidelines for Management of Adverse Events Associated with Atezolizumab and/or Tiragolumab

Table 4 Management Guidelines for Endocrine Events (cont.)

Event	Management

	
 • 

 • • • •

a

b

c

OCULAR EVENTS

An ophthalmologist should evaluate visual complaints (e.g., uveitis, retinal events). Management guidelines for ocular events are provided in [Table 5](#).

Appendix 16: Risks Associated with Atezolizumab and/or Tiragolumab and Guidelines for Management of Adverse Events Associated with Atezolizumab and/or Tiragolumab

Table 5 Management Guidelines for Ocular Events

Event	Management

	

	



	

a	

b	

c	

IMMUNE-MEDIATED CARDIAC EVENTS

Appendix 16: Risks Associated with Atezolizumab and/or Tiragolumab and Guidelines for Management of Adverse Events Associated with Atezolizumab and/or Tiragolumab

[REDACTED]. Management guidelines for cardiac events are provided in [Table 6](#).

IMMUNE-MEDIATED MYOCARDITIS

Immune-mediated myocarditis should be suspected in any patient presenting with signs or symptoms suggestive of myocarditis, including, but not limited to, laboratory (e.g., *troponin*, B-type natriuretic peptide) or cardiac imaging abnormalities, dyspnea, chest pain, palpitations, fatigue, decreased exercise tolerance, or syncope. Myocarditis may also be a clinical manifestation of myositis or associated with pericarditis (see section on *immune-mediated* pericardial disorders below) and should be managed accordingly. Immune-mediated myocarditis needs to be distinguished from myocarditis resulting from infection (commonly viral, e.g., in a patient who reports a recent history of gastrointestinal illness), ischemic events, underlying arrhythmias, exacerbation of preexisting cardiac conditions, or progression of malignancy.

[REDACTED]

Patients with signs and symptoms of myocarditis, in the absence of an identified alternate etiology, should be treated according to the guidelines in [Table 6](#).

IMMUNE-MEDIATED PERICARDIAL DISORDERS

Immune-mediated pericarditis should be suspected in any patient presenting with chest pain and may be associated with immune-mediated myocarditis (see section on *immune-mediated* myocarditis above).

[REDACTED]

[REDACTED]

Appendix 16: Risks Associated with Atezolizumab and/or Tiragolumab and Guidelines for Management of Adverse Events Associated with Atezolizumab and/or Tiragolumab

[figure not shown]
[figure not shown]
[figure not shown]
[figure not shown]
[figure not shown]
[figure not shown]
[figure not shown]
[figure not shown]
[figure not shown]
[figure not shown]
[figure not shown]

Table 6 Management Guidelines for Immune-Mediated Cardiac Events

Event	Management
	
• • • • • • 

INFUSION-RELATED REACTIONS

